10.3 Sensitivity Analyses

Efficacy analyses for the primary endpoints (PFS per CRAC and OS) will be performed in the Per Protocol Set.

Two sensitivity analyses will be carried out for PFS endpoint by implementing different censoring rules in the definition of PFS (i.e., modified PFS endpoint). These sensitivity analyses will be conducted in either DLL3^{high} Set or Randomized Set.

Sensitivity analysis 1: PFS will be defined as the number of months from randomization to disease progression, as assessed by the CRAC per RECIST v1.1, or death of any cause, whichever occurs first. Subjects without an event will be right-censored at the date of last follow up for disease progression. Patients with no post baseline follow up for progression and who doesn't experience a death event will be censored at the day of randomization.

Sensitivity analysis 2: PFS will be defined as the number of months from randomization to disease progression, as assessed by the CRAC per RECIST v1.1, or death of any cause, whichever occurs first. Subjects with 2 or more consecutive missed assessments (i.e., > 12 weeks since last scan) without any subsequent assessment prior to the PFS

event (i.e., progression or death) will be considered progressed at the planned date of the earliest missed scan date (i.e., last scan date prior to event + 6 weeks). Subjects without an event or receives new anti-cancer therapy will be right-censored at the date of last follow up for disease progression.

10.4 Subgroup Analyses

In the DLL3^{high} or randomized sets, treatment effects for the primary endpoints (PFS per CRAC and OS) will be assessed in the following subgroups:

- RECIST v1.1 response after completion of first-line platinum-based therapy at screening assessment (SD vs. PR/CR)
- DLL3 expression (Unknown vs. 0% to < 25% vs. 25% to < 75% vs. 75% or above) for the randomized set only
- History of CNS metastases (Yes vs. No)
- For subjects with no history of CNS metastases, PCI vs. No PCI
- Lactate dehydrogenase (LDH), \leq ULN vs. $>$ ULN
- Number of metastatic sites, 0 – 1 vs. $>$ 1
- Age group (age $<$ 40 vs. 40 to $<$ 65 vs. 65 or older)
- Gender
- Race
- ECOG (0 vs. 1)

The relationship between DLL3 expression level and outcome measures of OS and PFS by CRAC will be explored using additional subgroup analysis, as well as by multivariable Cox's model.

Differences between rovalpituzumab tesirine arm and the placebo arm for time-to-event endpoints will be assessed by an unstratified log-rank test for each subgroup. Hazard ratios of treatment arm over the placebo arm will be calculated by a Cox's model.

11.0 Safety Analysis

11.1 General Considerations

Unless otherwise specified, safety analyses will be performed on the Safety Set. No statistical comparisons will be performed between arms. No p-values and CIs will be provided.

Unless specified, all summaries/analyses involving AEs will only include treatment-emergent adverse events (TEAEs). TEAEs are defined as any adverse event with onset or increase severity after the first dose of study drug (rovalpituzumab tesirine or matching placebo; dexamethasone or matching placebo) and no more than 70 days after the last dose of study drug administration. AEs where the onset date is the same as the study drug start date are assumed to be treatment-emergent, unless the study drug start time and the AE start time are collected and the AE start time is prior to the study drug start time. If an incomplete onset date was collected for an AE, the AE will be assumed to be treatment-emergent unless there is evidence that confirms that the AE was not treatment-emergent (e.g., the AE end date was prior to the date of the first dose of study drug).

Adverse events will be coded and summarized by system organ class and preferred term (and severity) according to the Medical Dictionary for Regulatory Activities (MedDRA) version 21.0 or higher. The table of clinical toxicity grades modified from the National Cancer Institute Common Terminology Criteria for Adverse Events (NCI CTCAE) version 4.0 will be used in the grading of adverse events and laboratory abnormalities that are reported as adverse events.

Summary of continuous safety endpoints (e.g., change from baseline values in laboratory values, vital signs parameters) will include the mean, standard deviation, median and range. In the context of change from baseline analyses, summary of baseline and post-baseline data will also be provided. Categorical safety endpoints (e.g., incidence of AEs or clinically significant ECG values) will be summarized using frequencies and percentages. All the analyses will be carried out by treatment group.

Unscheduled assessment will not be included in the summary of change from baseline, but will be included in producing shift tables and summary of lab abnormalities.

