#### **Vital Signs**

Vital signs will be performed per Appendix C, Study Activities. Vital signs include actual weight, sitting blood pressure, heart rate and body temperature. If possible, blood pressure and heart rate measurements should not immediately follow scheduled blood collections.

Actual weight will be collected in the clinic prior to dosing at each cycle and the recorded weight will be utilized for dosing calculations. For weight assessments, the subject should not wear shoes. In the event of a 5% or greater increase in weight within 2 consecutive visits or compared to baseline which ever has the shorter interval, a prompt workup for fluid retention (e.g., edema, effusions, etc.) should be conducted. If weight gain is due to proven or suspected fluid retention related to study drug, and dosing is not prohibited per Section 5.5.4, dose should be calculated based on actual weight before the event of fluid retention.

Vital signs should be collected prior to the infusion.

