### Close observation includes:

- Repeating liver enzyme and serum bilirubin tests two or three times weekly.
   Frequency of retesting can decrease to once a week or less if abnormalities stabilize or the trial drug has been discontinued and the subject is asymptomatic.
- Obtaining a more detailed history of symptoms and prior or concurrent diseases
- Obtaining a history of concomitant drug use (including nonprescription medications and herbal and dietary supplement preparations), alcohol use, recreational drug use, and special diets

- Ruling out acute viral hepatitis types A, B, C, D, and E; autoimmune or alcoholic hepatitis; non-alcoholic steatohepatitis (NASH); hypoxic/ischemic hepatopathy; and biliary tract disease
- Obtaining a history of exposure to environmental chemical agents
- Obtaining additional tests to evaluate liver function, as appropriate (e.g., international normalized ratio [INR], direct bilirubin)
- Considering gastroenterology or hepatology consultations

Blinded investigational product will be discontinued if potential DILI is suspected and:

[figure not shown]
- ALT or AST  $> 8 \times ULN$
- ALT or AST  $> 5 \times ULN$  for more than 2 weeks
- ALT or AST  $> 3 \times ULN$  and (TBL  $> 2 \times ULN$  or INR > 1.5)
- ALT or AST  $> 3 \times$  ULN with the appearance of fatigue, nausea, vomiting, right upper quadrant pain or tenderness, fever, rash, and/or eosinophilia

All subjects showing possible DILI should be followed until all abnormalities return to normal or to the baseline state.

Any hepatic related adverse event should be recorded and the Hepatic Adverse Event eCRF triggered from the Adverse Event page.

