11.5 Analysis of Laboratory, Vital Signs, and ECG Data

Clinical laboratory variables are listed in [Table 4](#).

For laboratory (hematology, chemistry, urinalysis, and coagulation), vital signs, and ECG parameters, changes from baseline are analyzed for each post-baseline visit (as specified

in Section 6.0 Analysis of Conventions) and the final visit. If more than one measurement exists for a subject on a particular day, an arithmetic average will be calculated and considered to be the subject's measurement of that day.

Descriptive statistics will be presented for baseline, each post-baseline, and the final visit (the last valid record) by each treatment arm. Mean change from baseline to each post baseline visit, and to the final visit within each treatment arm will also be presented. The highest and lowest values of each parameter will be identified for each subject, and descriptive statistics for mean change from baseline within each treatment arm will be presented.

Laboratory grade determinations will be categorized according to NCI CTCAE version 4.0 grades, and shifts from baseline grades to maximum and final post-baseline grades will be assessed. The baseline and final grades will be defined respectively as the grade of the last measurement collected prior to or on the first dose of study drug, and as the grade of the last post-baseline measurement collected no more than 70 days after the last dose of study drug. Frequency and percentage of subjects will be presented by treatment arm: 1) baseline grade vs. maximum post-baseline grades, and 2) baseline grade vs. final post-baseline grade. Frequency and percentage of subjects experiencing a shift from baseline grades of 0 to 2 to maximum post-baseline grades of 3 to 4, and from baseline grades of 0 to 2 to final post-baseline grades of 3 to 4 will be presented by treatment arm.

Detailed listings of data for subjects experiencing NCI CTCAE grade 3 to 4 biochemistry and hematology values will be provided. All measurements collected, regardless of the number of days after the last dose of study drug, will be included in these listings. A listing will be provided for out-of-normal range as well as clinically significant abnormal lab values.

Descriptive summary statistics for categorical ECG status data will be presented for baseline and post-baseline visits. Shift tables will also be provided.

Table 4. Clinical Laboratory Tests

Hematology	Clinical Chemistry	Urinalysis (Dipstick)

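### The exclusion of unscheduled assessments in SAP 11.1 is not limited to by-visit means, so the highest/lowest change-from-baseline summary in SAP 11.5 would use scheduled values only

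*SAP*

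**What the plan says.** SAP 11.1 sets rules for the whole safety section. It gives as examples of continuous safety endpoints "change from baseline values in laboratory values, vital signs parameters". It then states: "Unscheduled assessment will not be included in the summary of change from baseline". The sentence goes on to keep unscheduled results in two places: "but will be included in producing shift tables and summary of lab abnormalities".

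SAP 11.5 covers laboratory, vital-sign and ECG parameters. It plans change from baseline at each visit and at the final visit. It also plans a summary of extremes: "highest and lowest values of each parameter will be identified for each subject, and descriptive statistics for mean change from baseline". It does not say whether unscheduled values count towards those extremes.

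The protocol calls for off-schedule attention when something is abnormal. Under close observation for possible liver injury (Protocol 6.1.8.3) it requires "Repeating liver enzyme and serum bilirubin tests two or three times weekly". For a weight increase of 5% or more, Protocol 5.3.1.1 (Vital Signs) says that "a prompt workup for fluid retention (e.g., edema, effusions, etc.) should be conducted". The Fluid Retention Questionnaire part of the same section has subjects contact the site about a sudden gain of that size for a possible clinic assessment.

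**The concern.** A table of each subject's highest and lowest value is meant to show how far a parameter moved. If it draws only on scheduled visits, it leaves out measurements that were taken because a value was already abnormal, and some of those will be the true extremes. The table would then report something other than its label says. A programmer following the SAP would have no ground for including the unscheduled values, and a reader of the report would have no way of knowing that they were left out.

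**Working it through.** The plan states no figure on this point, so the check sets the passages side by side.

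1. **Is the highest/lowest summary a change-from-baseline summary?** Yes. SAP 11.5 presents it as mean change from baseline within each arm.

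2. **Does the 11.1 exclusion reach it?** On the plain text, yes. The rule stands under General Considerations, refers to the change-from-baseline summary without naming by-visit means, and 11.5 states no exception.

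3. **Which direction does the effect take?** For one subject, the scheduled values are a subset of all values. The maximum of a subset cannot exceed the maximum of the full set, and its minimum cannot be lower. The exclusion therefore leaves each extreme unchanged or moves it towards less extreme. The effect is zero whenever a scheduled measurement already holds the extreme.

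4. **How far apart are scheduled measurements?** SAP Table 1 gives nominal Rx days 22, 43, 64, 85 and 127 for laboratory tests and vital signs. The spacing is 43 − 22 = 21 days, and 127 − 85 = 42 days around the omitted cycle.

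5. **How many liver retests could be left out?** Assume that close observation runs for a whole gap at the protocol's initial frequency. Then 21 days (3 weeks) gives 3 × 2 to 3 × 3 = 6 to 9 tests, and 42 days (6 weeks) gives 6 × 2 to 6 × 3 = 12 to 18 tests. This is an upper illustration, because Protocol 6.1.8.3 lets the frequency fall once values stabilise, or once the drug is stopped and the subject is asymptomatic. It counts results left out of the table and does not measure bias in the mean.

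6. **Where do unscheduled results survive?**

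| Data | Planned summary stated to use unscheduled results |
|---|---|
| Graded laboratory values | Shift to maximum grade and laboratory-abnormality summaries (11.1, 11.5); the grade 3 to 4 biochemistry and hematology listings in 11.5 include all measurements |
| ECG status | Shift tables (11.1, 11.5) |
| Blood pressure, pulse, temperature | None stated; 11.7 has criteria for these but is silent on unscheduled values |
| Body weight | None stated; no row in 11.7 |

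Weight belongs in this table because Protocol 5.3.1.1 collects it as a vital sign and Protocol 8.2.3 plans a change-from-baseline summary for it.

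**The case against.** The strongest reply is that the authors meant by-visit means only. SAP 11.5 lists the highest/lowest summary separately from the visit summaries and puts no scheduled-only limit on it. That may well be the intent, but nothing in either section says so, and the general rule comes first. If it is the intent, the fix only writes it down.

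A second reply is that scheduled values alone are a defensible choice. An extreme taken over more measurements tends to be larger, so including unscheduled values raises the extremes in whichever arm is tested more often. This is true and should be noted with the table. It is a small cost, because the maximum-grade shift tables already accept the same imbalance.

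A third reply concerns weight. The protocol's 5% trigger compares visits with each other or with baseline, so the raised weight will often already have been recorded at a clinic visit. The work-up it calls for looks for edema and effusions and does not specify another weighing. A reader might infer that peak weights fall at unscheduled visits; no passage shows that. What stands is narrower: if an unscheduled clinic weight is taken, no planned summary is stated to use it.

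A reader might also want to remove the same-day averaging in 11.5. SAP 6.1 assigns averages to continuous summaries and gives worst values as its shift-table example, so 11.5 is consistent with it.

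**Conclusion.** The point holds as a gap in specification with a one-directional consequence. As written, the highest/lowest change-from-baseline summary uses scheduled values only and can understate the size of extreme changes in laboratory values and vital signs, including weight. This rests on reading 11.1 at face value.

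The documents do not allow the understatement to be sized. A reader might try to derive it from the 21- and 42-day spacing, as the chance that a short excursion contains no scheduled draw. That would not measure what the rule loses. Liver retesting starts only after a raised value has been measured. If a scheduled draw found it, that value is already in the table; an excursion that no visit caught may have prompted no extra test either.

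A reader might also infer that the between-arm picture for liver toxicity or low blood counts would shrink. The documents do not support this. Unscheduled laboratory results stay in the graded summaries and listings, these toxicities and edema are also tracked as adverse events of special interest (SAP 11.3), and 11.1 plans no between-arm tests, p-values or confidence intervals. The effect is confined to the size of a descriptive mean. It matters most for vital signs and weight, which have no stated summary that keeps unscheduled values.

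**What to change.** - **SAP 11.1:** limit the exclusion to by-visit summaries. For example: *Unscheduled assessments are excluded from by-visit change-from-baseline summaries. They are included in the highest and lowest value summaries, shift tables and summaries of laboratory abnormalities.*
- **SAP 11.5:** state that each subject's highest and lowest values are taken from all post-baseline values, scheduled or unscheduled. Add a note that extremes will be somewhat larger where subjects are tested more often.
- **Local retests:** state how they are treated. Protocol 6.1.8.3 allows liver retests at a local laboratory and requires the data to be recorded in the CRF, while Protocol 5.3.1.1 (Clinical Laboratory Tests) reserves central-laboratory data for analysis. Without this statement, local retests could still be left out after the edit.

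The cost is a few sentences in the SAP, which under SAP 3.0 is to be finalised before unblinding. No new data collection is needed and no efficacy analysis changes.

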11.2 Analysis of Adverse Events

The number and percentage of subjects having treatment-emergent adverse events will be tabulated by MedDRA system organ class (SOC) and preferred term (PT) for each treatment group. Subjects reporting more than one adverse event for a given MedDRA PT will be counted only once for that term. Subjects reporting more than one type of adverse event within a MedDRA SOC will be counted only once for that SOC. Subjects reporting more than one type of adverse event will be counted only once in the overall total.

The tabulations will also be provided with further breakdowns by maximum severity per NCI CTCAE v4.0 grade. If a subject has an AE with unknown severity, then the subject will be counted in the severity category of "unknown," unless the subject does not have another occurrence of the same AE with a severity present. If a subject has multiple occurrences of an AE with the same organ class and preferred term, the most severe event will be presented.

Adverse events possibly related to study drug (rovalpituzumab tesirine or dexamethasone) as assessed by the investigator in each treatment arm. If a subject has an AE with unknown relationship, then the subject will be counted in the relationship category of "unknown," unless the subject does not have another occurrence of the same AE with a relationship present.

Serious adverse events, adverse events leading to dose reduction, discontinuation of treatment, and adverse events leading to death will be summarized.

An overview of AEs will be presented, by treatment arm and overall, consisting of the number and percentage of subjects experiencing the following adverse event categories:

- Any treatment-emergent adverse event

- Any treatment-emergent adverse event NCI toxicity grade 3 or 4
- Any treatment-emergent adverse event that is rated as a reasonable possibility of being related to study drug
- Any treatment-emergent adverse event NCI toxicity grade 3 or 4 that is rated as a reasonable possibility of being related to study drug
- Any treatment-emergent serious adverse event
- Any treatment-emergent serious adverse event NCI toxicity grade 3 or 4
- Any treatment-emergent serious adverse event that is rated as a reasonable possibility of being related to study drug
- Any treatment-emergent adverse event leading to discontinuation of rovalpituzumab tesirine
- Any treatment-emergent adverse event leading to delay/interruption of rovalpituzumab tesirine
- Any treatment-emergent adverse event leading to reduction of rovalpituzumab tesirine
- Any treatment-emergent adverse event leading to death
- Any treatment-emergent adverse event leading to death that is rated as a reasonable possibility of being related to study drug
- Any treatment-emergent serious adverse event leading to discontinuation of rovalpituzumab tesirine
- Any treatment-emergent serious adverse event leading to delay/interruption of rovalpituzumab tesirine
- Any treatment-emergent serious adverse event leading to reduction of rovalpituzumab tesirine
- Any treatment-emergent serious adverse event leading to death

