4.3 Randomization and Stratification

All subjects in the study will be randomized using an IRT system. The site will contact the IRT to obtain a Screening (subject) number once the subject has signed the informed consent. Once the screening number is assigned, if the subject is not eligible to be randomized into the study, the reason for screen failure will be documented in the source document and in the eCRF. For others, the site will access the system and a unique randomization number will be provided.

The IRT will randomize subjects in a 1:1 ratio to the rovalpituzumab tesirine treatment arm or to the placebo arm. The stratification factors used for the randomization should be the last values on or prior to the date of randomization.

The stratification factors are:

- RECIST v1.1 response after completion of first-line platinum-based therapy at screening assessment (SD vs. PR/CR),
- DLL3 expression (Unknown vs. 0% to < 25% vs. 25% to < 75% vs. 75% or above),
- History of CNS metastases (Yes vs. No),
- For subjects with no history of CNS metastases, PCI vs. no PCI.

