4.4 Sample Size

There are two primary efficacy endpoints for this study: Progression-free survival (PFS) based on the CRAC and overall survival (OS) in DLL3^{high} ED SCLC subjects. To maintain the overall 1-sided type I error rate at a 2.5% for this study, the type I error will be split, assigning 0.25% to progression-free survival and the remaining 2.25% to overall survival. However, the OS endpoint will be tested as a one-sided 2.2499% significance level as a one-sided alpha of 10^{-6} will be spent for the early look at the OS data for futility analysis.

Sample size of the study is primarily determined by the analysis of OS. It is assumed, taking into account the expected patient population for the study, that median overall survival in the placebo and rovalpituzumab tesirine arm will be around 9 months and 13 months, respectively. The increase of median OS in rovalpituzumab tesirine arm corresponds to a hazard ratio of 0.69, i.e., a reduction in the hazard of death by 31%. With all these assumptions, a total of 319 deaths among subjects with DLL3^{high} are needed to achieve 90% power based on a log-rank test at a one-sided significance level of 0.022499. Assuming a 19-month accrual period and the last enrolled subject followed for 12 months, at least 480 subjects with DLL3^{high} are expected to be randomized (240 subjects in each arm). A total of 740 subjects regardless of DLL3 expression level (including 480 subjects with DLL3^{high}) will enroll in the study, assuming an approximate prevalence of 65% for subjects with DLL3^{high}.

The primary endpoints of OS and PFS will be analyzed at the same time after observing at least 319 OS events in subjects with DLL3^{high}. It is expected that approximately 420 PFS events assessed by the CRAC will be observed at the time of the primary analysis.

It is assumed, taking into account the expected patient population for the study, that median progression-free survival for the placebo and rovalpituzumab tesirine arm will be approximately 3 months and 4.5 months, respectively. The increase of median progression-free survival in rovalpituzumab tesirine arm corresponds to a hazard ratio of 0.667. With all these assumptions, a total of approximately 420 PFS events assessed by the CRAC for the subjects with DLL3^{high} are needed to achieve 91% power based on a log-rank test at a one-sided significance level of 0.0025.

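### Apart from a median time to onset for AESIs, adverse events are compared only as crude percentages, although the plan's own PFS assumption gives Rova-T about 37% more time at risk

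*SAP*

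**What the plan says.** SAP 11.2 states: "The number and percentage of subjects having treatment-emergent adverse events will be tabulated by MedDRA system organ class (SOC) and preferred term (PT". The breakdowns by grade and the overview of event categories are also counts and percentages of subjects. SAP 11.1 sets the same rule for categorical safety endpoints generally, shown by treatment group with no statistical comparison between arms. It counts an event as treatment-emergent if it begins or worsens after the first dose and "no more than 70 days after the last dose of study drug administration".

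The Protocol synopsis (Duration of Treatment) has dosing on Day 1 of 6-week cycles, every third cycle omitted, until progression. SAP 4.4 assumes that "median progression-free survival for the placebo and rovalpituzumab tesirine arm will be approximately 3 months and 4.5 months, respectively".

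Two other provisions bear on the point. SAP 9.0 tabulates duration of treatment, cumulative dose and dose intensity. SAP 11.3 analyses time to onset of AESIs by Kaplan-Meier. Subjects without an event are censored at the earlier of their last assessment and 70 days after the last dose, and the median is reported with its confidence interval. Neither document plans events per unit of patient-time, or cumulative incidence at a fixed time.

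**The concern.** A crude percentage compares arms fairly when subjects are observed for similar lengths of time. Here the observation window depends on how long treatment lasts, and treatment lasts until progression. If the drug delays progression as the trial is powered to show, Rova-T subjects are watched for longer and collect more events that have nothing to do with the drug.

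This matters most for events with a background rate in both arms. Pleural effusion is an important identified risk in SAP Table 3 and is also listed in Protocol Appendix J as expected from SCLC. Dyspnoea, fatigue and decreased appetite are in Appendix J too. For such events a higher Rova-T percentage could reflect drug effect, longer observation or both, and the percentages alone do not say which.

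**Working it through.** **The plan's own figures.** For PFS, SAP 4.4 says the difference in medians "corresponds to a hazard ratio of 0.667" and that about 420 events "are needed to achieve 91% power based on a log-rank test at a one-sided significance level of 0.0025". By Schoenfeld's formula, power = Φ(½√420 × ln 1.5 − 2.807) = Φ(4.155 − 2.807) = 0.911. For OS, 319 deaths with medians 9 and 13 months: Φ(½√319 × ln(13/9) − 2.005) = Φ(3.284 − 2.005) = 0.900. Both stated powers reproduce, so the medians are a sound basis. The documents give no figure for time at risk.

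**Inputs.** PFS medians 3 and 4.5 months; 1 month = 30.4375 days (SAP 10.1.1); infusions on days 0, 42, 126, 168, 252, 294 and so on; window ends at last infusion + 70 days. Assumptions of mine: exponential PFS and treatment stopping only at progression.

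**Daily PFS hazard**, r = ln 2 / median:
- Placebo: 0.6931 / 91.31 = 0.007591
- Rova-T: 0.6931 / 136.97 = 0.005061

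**Mean window.** Gaps between infusions alternate 42 and 84 days, and a dose on day d is given with probability exp(−r·d). The mean is therefore

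70 + [42·exp(−42r) + 84·exp(−126r)] / [1 − exp(−126r)]

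- Placebo: 70 + (42 × 0.7270 + 84 × 0.3842) / 0.6158 = 70 + 102.0 = 172 days
- Rova-T: 70 + (42 × 0.8085 + 84 × 0.5285) / 0.4715 = 70 + 166.2 = 236 days
- Ratio: 236.2 / 172.0 = 1.37

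Simulation that also ends the window at death, with OS medians 9 and 13 months, gives 168 and 234 days, ratio 1.39. Time to progression plus 70 days gives 1.33; time to progression alone gives 1.50.

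**Effect on crude percentages.** With one constant event rate λ in both arms, the expected percentage is the mean of 1 − exp(−λ × window). I set λ to give a chosen placebo percentage and applied it to Rova-T. For 20% on placebo, λ = 0.00138 per day, about 50 per 100 patient-years.

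| Placebo | Rova-T, same rate | Ratio |
|---|---|---|
| 1% | 1.4% | 1.37 |
| 5% | 6.7% | 1.35 |
| 10% | 13.2% | 1.32 |
| 20% | 25.5% | 1.28 |
| 30% | 37.0% | 1.23 |
| 50% | 57.8% | 1.16 |

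An exposure-adjusted rate would give a ratio of 1.0 in every row.

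**Sensitivity to toxicity stopping.** The documents allow it but give no rate. Adding it on Rova-T only, with an assumed median time to such stopping:

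| Median (months) | 36 | 24 | 12 | 9 | 6 |
|---|---|---|---|---|---|
| Window ratio | 1.25 | 1.20 | 1.07 | 1.00 | 0.90 |

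**The case against.** **Time is not ignored.** The AESI time-to-onset analysis handles unequal follow-up and covers the risks that matter most, so it would be wrong to infer that every safety summary lacks a time element. That stands. Its limit is that only a median is promised. The Rova-T percentages in Protocol 3.5 are all below 50% for these risks: pleural effusion 33.9%, photosensitivity 27.7%, pericardial effusion 16.7%, pneumonitis 1%. A median will generally not be reached at such levels, though a Kaplan-Meier estimate runs above the crude figure and cutaneous reactions, at 48.7%, might reach it. SAEs, Grade 3 or higher events and the SOC/PT tables have no such analysis.

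**Exposure is tabulated and nothing is tested.** Also true, so the difference in exposure will be visible. But SAP 9.0 reports treatment weeks, not the treatment-emergent window, and does not link them to event counts. Tables shown by arm will be read side by side with or without a p-value.

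**Not every event is inflated.** A reader might infer that all percentages rise on Rova-T, including events caused by the cancer. The documents do not support that. Protocol 6.1.1.3 has progression reported through its manifestations, such as brain metastases. If progression is delayed, the hazard of those events falls and the equal-hazard calculation does not apply.

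**The direction is not fixed.** The sensitivity table shows that enough toxicity stopping removes or reverses the imbalance. This argues for prespecifying a time denominator, but it rules out saying that the tables will be biased against Rova-T.

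**Rates can mislead too.** If toxicity clusters after the first doses and the percentages are equal, a window ratio of 1.37 makes the Rova-T rate look up to 27% lower (1 − 1/1.37). This stands, and is why rates should not replace percentages.

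**Conclusion.** The gap is real and modest. Outside the AESI median, the planned adverse event tables give no means of separating event risk from length of observation. Under the trial's own PFS hypothesis the mean window is about 37% longer on Rova-T. The resulting excess depends on background incidence: from about 37% for rare events to 16% for an event at 50%. No single figure covers all events, and the documents give no placebo incidences.

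These sizes rest on exponential PFS, a constant event hazard equal in both arms, and stopping only at progression. Apart from deaths, every treated subject has at least 70 days of window, so events confined to that period are little affected. The medians apply to DLL3-high subjects, while the Safety Set is all treated subjects.

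One caution on absolute days: adding a separate death hazard that also stops treatment shortens the windows to about 129 and 175 days. PFS already includes death, so that counts deaths twice; the ratio stays near 1.36.

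**What to change.** In SAP 11.2 and 11.3, beside n (%), add exposure-adjusted incidence rates: subjects with the event per 100 patient-years, with time counted to the first event or the end of the treatment-emergent window. Do this for the overview rows, SAEs, Grade 3 or higher TEAEs and AESIs. For AESIs, also report cumulative incidence by arm at fixed times, with death as a competing event, so that the time-to-onset analysis gives a usable result when no median is reached. State in SAP 11.1 that rates and percentages are to be interpreted together.

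The cost is a few more table columns and the programming for them. Dosing, onset and death dates are already collected, and the SAP is to be finalised before unblinding. The rates assume a roughly constant hazard, which is why the percentages stay.
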